3.3. Dose Rationale

Based on the nonclinical studies conducted to date and the available clinical data, the 80-mg dose is considered a dose with a sufficient safety margin to be evaluated in patients with DLB or PDD who experience RBD behaviors.

4. OBJECTIVES AND ENDPOINTS

Objectives	Endpoints
Primary	
To assess the effects of nelotanserin versus placebo on the frequency per 10 minutes of REM sleep of characteristic RBD behaviors (sum of simple/major and complex RBD events) in the DLB patient subgroup based on video/audio assessment conducted at a sleep laboratory	The change in frequency per 10 minutes of REM sleep of characteristic RBD behaviors (sum of simple/major and complex RBD events) from baseline (the whole-night sleep study during placebo run-in period) to end of study (EOS) (the whole-night sleep study at the EOS) in the DLB patient subgroup
Key Secondary	
To assess the effects of nelotanserin versus placebo on extrapyramidal symptoms in the DLB patient subgroup based on UPDRS Part III score	The change in UPDRS Part III score from baseline (V4) to EOS (V5/ET) in the DLB patient subgroup
To assess the effects of nelotanserin versus placebo on the frequency per 10 minutes of REM sleep of characteristic RBD behaviors (sum of simple/minor, simple/major, and complex RBD events) in the DLB patient subgroup based on video/audio assessment conducted at a sleep laboratory	The change in frequency per 10 minutes of REM sleep of characteristic RBD behaviors (sum of simple/minor, simple/major, and complex RBD events) from baseline (the whole-night sleep study during placebo run-in period) to end of study (EOS) (the whole-night sleep study at the EOS) in the DLB patient subgroup
Other Secondary	
To assess the effects of nelotanserin versus placebo on in the DLB patient subgroup based on UPDRS Part II (activities of daily living), UPDRS Parts II+III, UPDRS 5-item scores	The change in UPDRS Part II, II+III and UPDRS 5-item scores from baseline (V4) to EOS (V5/ET) in the DLB patient subgroup
To assess the effects of nelotanserin versus placebo on frequency and severity of RBD behaviors (sum of simple/minor, simple/major, and complex RBD events) in the DLB patient subgroup based on video/audio assessment conducted at a sleep laboratory	The change in the proportion of RBD behaviors rated as severe and the composite score based on both severity and frequency of RBD behaviors (sum of simple/minor, simple/major, and complex RBD events) from baseline (V3) to EOS (V5/ET) in the DLB patient subgroup

To assess the effects of nelotanserin versus placebo on both severity and frequency of RBD behaviors (sum of simple/minor, simple/major, and complex RBD events) in the DLB patient subgroup based on video/audio assessment conducted at a sleep laboratory	The change in the composite score based on both severity and frequency of RBD behaviors (sum of simple/minor, simple/major, and complex RBD events) from baseline (V3) to EOS (V5/ET) in the DLB patient subgroup
To assess the effects of nelotanserin versus placebo on the number of injuries to the subject or bed partner in the DLB patient subgroup as recorded on the study diary completed by the subject and/or bed partner/caregiver	The change in the number of nights with injurious behaviors to the subject or bed partner per week from baseline (Week 0) to EOS (Week 4) in the DLB patient subgroup
To assess the effects of nelotanserin versus placebo on presence, frequency and severity of sleep behaviors in the DLB patient subgroup as recorded on the study diary completed by the subject and/or bed partner/caregiver	The change in the number of nights with no sleep movements and/or vocalizations per week, the nightly number of sleep movements and/or vocalizations per week, the nightly severity of sleep movements and/or vocalizations per week, and a composite score based on nightly number and severity of sleep movements and/or vocalizations per week from baseline (Week 0) to EOS (Week 4) in the DLB patient subgroup.
To assess the effects of nelotanserin versus placebo on subjective sleep quality in the DLB patient subgroup based on scores from the Scales for Outcomes in Parkinson's disease (SCOPA) – Sleep	The change in SCOPA–Nighttime Sleep (NS) problems and Daytime Sleepiness (DS) subscale scores from baseline (V4) to EOS (V5/ET) in the DLB patient subgroup
To assess the effects of nelotanserin versus placebo on quality of bed partner sleep in the DLB patient subgroup as measured by a visual analog scale (VAS) completed by the bed partner	The change in quality of bed partner sleep as measured by a VAS completed by the bed partner from baseline (V4) to EOS (V5/ET) in the DLB patient subgroup
To assess the effects of nelotanserin versus placebo on clinicians' rating of change in RBD behaviors in the DLB patient subgroup as measured by Clinicians' Global Impression of Change in RBD Behaviors (CGIC-RBD)	The comparison of CGIC-RBD at EOS (V5/ET) in the DLB patient subgroup

To assess the effects of nelotanserin versus placebo on objective sleep parameters during the night and surface electromyography (EMG) parameters during REM sleep, in the DLB patient subgroup obtained using polysomnography (PSG) at a sleep laboratory	The change in objective sleep and EMG parameters from baseline (V3) to EOS (V5/ET) in the DLB patient subgroup
To assess the effects of nelotanserin versus placebo on physical activity during sleep in the DLB patient subgroup as measured by the ActiGraph activity monitor	The total count of movements during sleep as measured by the ActiGraph activity monitor from baseline (Week 0) to EOS (Week 4) in the DLB patient subgroup
Safety	
To assess the safety of nelotanserin in all patients and in DLB and PDD subgroups	Safety will be assessed by analyzing adverse events (AEs), laboratory values, vital signs, and physical examinations. Cognitive functioning will be assessed with the Montreal Cognitive Assessment (MoCA) scale and the Mini-Mental State Examination (MMSE).
Pharmacokinetic	
To assess the steady-state plasma exposure of nelotanserin and M1 metabolite and the relationship to primary endpoint	Plasma nelotanserin and M1 metabolite concentration on Visit 5 Descriptive analysis of the relationship between plasma nelotanserin and M1 concentrations and the change in nightly frequency of RBD behaviors

In addition, several exploratory evaluations will be analyzed for efficacy in the DLB patient subgroup, the PDD patient subgroup, and all patients. Details of exploratory objectives and endpoints are outlined in the Statistical Analysis Plan.

5. STUDY DESIGN

5.1. Overall Design

This is a multicenter, double-blind, randomized, placebo-controlled study in DLB or PDD subjects with RBD. The study will be conducted at approximately 25 sites.

[figure not shown]
Following an initial screening period, eligible subjects will be given ActiGraph activity monitors at run-in visit (V2) to wear nightly throughout the course of the study (including sleep laboratory nights), and subjects and their caregivers/bedpartners will record sleep behaviors on a diary throughout the study. Subjects will then enter a single-blind placebo run-in period of up to 30 days in duration during which baseline video-PSG will be obtained at a sleep laboratory (baseline/Visit 3). To allow subjects to be acclimated to the sleep laboratory environment, subjects will spend a minimum of 2 (preferably consecutive) nights at the sleep laboratory. To be eligible for randomization, the subject must have at least one qualifying night which is defined as a night with all of the following criteria met: 1) a total REM sleep duration ≥ 10 minutes based on PSG assessment, 2) at least 4 RBD events per 10 minutes of REM per night based on video/audio review, and 3) at least one simple/major or complex RBD event per night based on video/audio review. At the end of the single-blind placebo run-in period, all subjects who continue to meet the eligibility criteria will enter a 4-week double-blind treatment period. Each subject will be randomized 1:1 to either nelotanserin 80 mg or matching placebo. For subjects assigned to nelotanserin 80 mg, the dose will be titrated up to the 80-mg dose strength in a blinded fashion after initial 5 days of treatment with 40 mg nelotanserin. Subjects will be assessed for primary efficacy using a whole-night video-PSG for at least 2 nights at a specified sleep laboratory again after approximately 4 weeks of the double-blind treatment (end of study [EOS]/Visit 5).

Following the final visit, subjects who have completed the study may be eligible to participate in an open-label extension study with nelotanserin. The study design is outlined in [Figure 1](#) **Error! Reference source not found.**

The primary objective is to assess the effects of nelotanserin versus placebo on the frequency per 10 minutes of REM sleep of characteristic RBD behaviors (sum of simple/major and complex RBD events) for the DLB patient subgroup, based on video/audio assessment conducted at a sleep laboratory.

The key secondary objectives are to assess the effects of nelotanserin versus placebo on extrapyramidal symptoms based on the UPDRS Part III score, and to assess the effects of nelotanserin versus placebo on frequency of characteristic RBD behaviors (sum of simple/minor, simple/major, and complex RBD events) based on video/audio assessment conducted at a sleep laboratory, for the DLB patient subgroup.

Figure 1. Study Design

6. SUBJECT POPULATION

6.1. Type and Number of Subjects

The study will randomize approximately 52 subjects with DLB and PDD (with approximately 34 DLB subjects) who experience frequent RBD behaviors prior to screening and meet randomization criteria (Section 6.2.3) during 1 or more qualifying night(s) in the single-blind placebo run-in period (based on a central review of video-PSG data obtained from the sleep laboratory):

Nelotanserin 80 mg - 26 subjects

Placebo - 26 subjects.

6.2. Key Inclusion/Exclusion Criteria

6.2.1. Inclusion Criteria

1. Adult subjects at least 50 years of age with a diagnosis of probable major neurocognitive disorder (dementia) with Lewy bodies (DLB) based on the Diagnostic and Statistical Manual of Mental Disorders version 5 (DSM-5) diagnostic criteria or diagnosis of Parkinson's disease dementia (PDD) based on DSM-5 diagnostic criteria;
2. Subjects with a concurrent diagnosis of REM sleep behavior disorder (RBD) based on DSM-5 criteria and who have reported frequent RBD episodes prior to Screening (Visit 1);
3. Either MMSE score ≥ 18 or MoCA score ≥ 12 ;
4. Stable antipsychotic treatments will be allowed if taken at a stable dosage of ≤ 25 mg/day quetiapine or equivalent (see Appendix 13.4) for at least 4 weeks prior to screening and if dosage and regimen is expected to remain stable throughout the study;
5. Low dose clonazepam (≤ 1 mg/day) or melatonin treatment (any dose) will be allowed if at a stable dosage for at least 4 weeks prior to screening and if dosage and regimen is expected to remain stable throughout the study, regular use of other benzodiazepines other than clonazepam may be permitted if approved by the medical monitor;
6. Subjects taking anti-Parkinson drugs (eg, levodopa) or anti-Parkinson treatment (eg, deep brain stimulation) must be on stable regimen for at least 4 weeks prior to screening and expected to continue the stable regimen throughout the study;
7. Subjects taking acetylcholinesterase inhibitors (AChEIs) or memantine must be on stable dosage for at least 4 weeks prior to screening and expected to continue the stable regimen throughout the study;
8. Subjects must have a caregiver or family member who can serve as a collateral informant for study assessments and, if necessary, provide proxy consent to participate in the study;
9. Females who
 - a. have undergone surgical removal of the uterus or removal of both ovaries, or
 - b. have been naturally postmenopausal for at least 24 consecutive months (ie, no menses at any time during the preceding 24 consecutive months).

6.2.2. Exclusion Criteria

1. Subjects' sleep behavioral symptoms are secondary to or better accounted for by another psychiatric disorder (eg, other non-REM parasomnias, multiple system atrophy) or substance abuse (eg, alcoholism);
2. Subjects who have a current diagnosis of significant psychotic disorders including, but not limited to, schizophrenia or bipolar disorder;
3. Any significant change in the subject's environment within the past 4 weeks;
4. Subjects with a history of significant cerebrovascular events;
5. Subjects with a current serious and/or unstable cardiovascular, respiratory, thyroid, gastrointestinal, hepatic, biliary, renal, hematologic, or other serious medical disorder that would preclude participation in the study;
6. Use of any antipsychotic medication at a dosage of >25 mg/day quetiapine or equivalent (see [Appendix 13.4](#));
7. Subjects with a history of alcohol use disorder or other substance abuse disorder (excluding tobacco use) in the past 10 years, or a positive Urine Drug Screen unless explained by physician prescribed and stable medication;
8. Subjects with current use of sedative-hypnotic medication (other than stable low dose clonazepam or any dose of melatonin), regular use of other benzodiazepines other than clonazepam may be permitted if approved by the medical monitor;
9. Subjects with medication-induced RBD or receiving venlafaxine or mirtazapine that may induce RBD behaviors;
10. Subjects with current use of anti-epileptic medication for seizures or a history of seizures within the past 18 months;
11. Subjects who are allergic or hypersensitive to nelotanserin;
12. Subjects who have used any investigational medication within 30 days prior to the first dose of study medication.
13. Subjects who have used pimavanserin within 30 days prior to the first dose of study medication;
14. Use of any concomitant medications as detailed in [Table 1](#). Prohibited medications as outlined in [Table 1](#) unless otherwise specified, need to have been discontinued for 5 half-lives prior to screening and assessed as no longer clinically necessary for the subject;
15. Subjects who have significant suicide risk defined by suicidal ideation as endorsed on items 4 or 5 of the Columbia Suicide Severity Rating Scale ([C-SSRS](#)) at screening of this study or who have clinical assessment of significant suicidal risk.
16. Subjects with a history of significant hepatic and biliary disorders such as viral hepatitis, or liver cirrhosis;
17. Subjects with a history of Gilbert's Syndrome, Dubin-Johnson Syndrome, Rotor Syndrome, Familial Intrahepatic Cholestasis, Gaucher's disease, or other inherited metabolic diseases that have the potential to effect hepatic function should be discussed with the medical monitor;
18. Subjects with aspartate transaminase (AST), alanine transaminase (ALT), or serum total bilirubin level (TBL) test values greater than the upper limit of the laboratory reference (normal) range (ULN);
19. Subjects with prothrombin time (PT)/international normalized ratio (INR) greater than the ULN, – subjects receiving warfarin or coumadin and an INR <3 may be allowed to participate if approved by the medical monitor;

20. Subjects who have a clinically significant abnormality in other clinical laboratory results or other clinical conditions that, in the opinion of the investigator/medical monitor, would prevent the subject from safely participating in this study.

6.2.3. Additional Randomization Criteria

In addition, subjects must satisfy the following criteria during the placebo run-in period to be randomized in the study:

1. Subjects must at least one qualifying night which is defined as a night with all of the following criteria met:
 - a. a total REM sleep duration of ≥ 10 minutes based on PSG assessment;
 - b. at least 4 RBD events per 10 minutes of REM per night based on video/audio review
 - c. at least one simple/major or complex RBD events per night based on video/audio review;
2. Subjects who have overall Apnea Hypopnea Index [AHI] and REM AHI < 20 /hour.

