Subjects will wear ActiGraph activity monitors on both of their wrists during sleep throughout the study, both at home and during the sleep laboratory nights.

Subjects and their caregivers/bedpartners will record sleep behaviors on the diary throughout the study.

A minimum of 14 days of placebo run-in is required prior to Visit 3 sleep laboratory assessments.

Visit 3 sleep laboratory assessments and confirmation of eligibility (See [Section 6.2](#)) are required prior to Visit 4 baseline/randomization.

Baseline Sleep Laboratory Visits (Visit 3 – up to 10 days)

At Visit 3, after the subject completes at least 2 weeks of placebo run-in treatment (ie, at least 14 days post Visit 2), the subject will participate in a whole-night video-PSG study at a specified sleep laboratory, during which his/her RBD behaviors will be evaluated while continuing his/her placebo treatment.

To allow subjects to acclimate to the sleep laboratory environment, subjects will spend a minimum of 2 (preferably consecutive) nights at the local sleep laboratory. During this study, the subject must have at least one qualifying night of REM sleep. A qualifying night of REM sleep is defined as a night with REM sleep duration of ≥ 10 minutes (total, not necessarily consecutive). If a subject cannot achieve one or more qualifying nights of REM sleep, the video-PSG study may be repeated for up to 2 nights as unscheduled visit(s). All sleep lab night assessments (maximum of 4 nights including unscheduled visits) must be completed within 10 days of Visit 3 (ie, first baseline sleep lab night).

The video-PSG data will be reviewed by central reviewers to determine if the subject meets the randomization criteria (See [Section 6.2](#)). During this time, the subject will continue to receive placebo until being notified to return for the next visit.

Management of patients with OSA and CSA:

During the baseline sleep laboratory visits (V3), for subjects who have overall AHI and REM AHI < 20 /hour

1. Subjects are allowed to continue in the trial if they a) per investigator's discretion, do not require initiation of treatment (eg, CPAP) and can remain untreated throughout the trial, b) need treatment adjustments and can remain on the same adjusted treatment regimen throughout the trial (eg, CPAP or alternative positive air pressure device, such as bilevel positive airway pressure or adaptive servoventilation).

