2. Treatment naïve subjects (ie, previously not treated for OSA/CSA) are not allowed to continue in the trial at this time if initiation of treatment is deemed necessary by the investigator. Subjects will be considered as run-in failures. After stable treatment and satisfactory adherence to treatment is established for at least 2 weeks ([Section 6.5.1](#)), subjects may be considered for participating in the study for the second and final time. All screening procedures must be repeated.

For subjects who have overall AHI or REM AHI ≥ 20 per hour during baseline sleep laboratory visits (V3)

1. If already receiving treatment for OSA/CSA at entry of the trial, subjects may still continue if upon treatment adjustment, an overall AHI and REM AHI <20/hour can be achieved. Subjects should remain on the same adjusted treatment regimen throughout the trial.
2. Treatment naïve subjects (ie, previously not treated for OSA/CSA) are not allowed to continue in the trial at this time. Subjects will be considered as run-in failures. After stable treatment and satisfactory adherence to treatment is established for at least 2 weeks ([Section 6.5.1](#)), subjects may be considered for participating in the study for the second and final time. All screening procedures must be repeated and subject will be assigned a new screening number. For these subjects, the baseline sleep laboratory visits (V3) for the second time must confirm that overall AHI and REM AHI <20 per hour for at least one of the 2 nights in order to proceed with the trial.

Double-blind Treatment Period (Period B – up to 40 days)

Baseline/Randomization (Visit 4 – Day 0)

At Visit 4 (Day 0), prior to ingestion of double-blind investigational product, baseline assessments will be performed to determine subject eligibility.

To qualify for randomization at Visit 4, subjects must meet protocol-specified criteria for RBD behaviors at baseline, return unused study medication, be considered capable of completing study assessments, and continue to meet all other eligibility requirements.

Eligible subjects will be randomized 1:1, stratified by status (presence/absence) of background treatment with clonazepam (or other benzodiazepines) and/or melatonin and by disease type (DLB or PDD), to either the nelotanserin 80 mg treatment group or the placebo group.

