8.2. Critical Baseline Assessments

Subjects need to continue to meet the eligibility criteria for REM sleep behaviors:

A subject must experience frequent RBD episodes prior to Screening (Visit 1). In addition, there must be at least four (4) RBD episodes (one or more of which must include simple/major or complex RBD events) per 10 minutes of REM sleep during 1 or more qualifying night(s) based on a central review of video-PSG data obtained from the sleep laboratory during the single-blind placebo run-in period. The subject also needs to have overall AHI and REM AHI <20/hour.

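### Does Section 8.2 set a stricter randomisation rule than Section 6.2.3 by tying the simple/major or complex event to each 10 minutes of REM sleep?

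*Combined protocol and SAP*

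**What the plan says.** Section 6.2.3 lists three limbs for a qualifying night: total REM of 10 minutes or more, at least 4 RBD events per 10 minutes of REM, and "at least one simple/major or complex RBD events per night based on video/audio review". The third limb is a count for the whole night and stands apart from the rate in the second. Section 5.1 has the same limb, "at least one simple/major or complex RBD event per night based on video/audio review", and the synopsis matches it.

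Section 8.2 opens with "Subjects need to continue to meet the eligibility criteria for REM sleep behaviors" and then compresses the two event limbs into one sentence: "at least four (4) RBD episodes (one or more of which must include simple/major or complex RBD events) per 10 minutes of REM sleep". The sentence goes on to say that this must hold on one or more qualifying nights, judged by central review of the run-in recordings.

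Other sections say where the rule is kept. Section 6.1 cites Section 6.2.3 by number for the randomisation criteria. In Section 8.1, sleep-laboratory assessments and confirmation of eligibility, with a pointer to Section 6.2, "are required prior to Visit 4 baseline/randomization". The recordings are "reviewed by central reviewers to determine if the subject meets the randomization criteria", again with a pointer to Section 6.2. The Visit 4 text says "subjects must meet protocol-specified criteria for RBD behaviors at baseline" and names no section.

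**The concern.** In Section 8.2 the requirement for a simple/major or complex event sits inside a phrase that ends with the 10-minute rate. If the rate is taken to govern the parenthesis too, the night needs at least one such event per 10 minutes of REM. That is a second, stricter threshold than the one in Section 6.2.3.

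The criterion decides who is randomised, and the events concerned are those the primary endpoint counts. A subject could be properly randomised under Section 6.2.3 and look ineligible under Section 8.2. Section 8 allows no waivers except for immediate safety concerns, Section 6.5.1 lists failing eligibility at Visit 4 among possible reasons for withdrawal, and Section 10.3.1 removes subjects with major protocol deviations from the per-protocol set. If sites or central reviewers used different rules, the enrolled population would be less clearly defined.

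**Working it through.** **Inputs.** REM minimum of 10 minutes, 4 events per 10 minutes, and one simple/major or complex event per night (Section 6.2.3); the merged sentence (Section 8.2). The documents give no typical REM duration or event rate, so every duration above 10 minutes below is illustrative.

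**Step 1: size of the gap under each reading.** Let R be minutes of REM on the night.

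- Section 6.2.3: 1 event, whatever R is.
- Section 8.2, rate reading: R/10, rounded up.
- Section 8.2, ordinary reading (some of the night's episodes must be of this kind): 1 event, whatever R is.

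| R (min) | 6.2.3 | 8.2, rate reading | 8.2, ordinary reading |
|---|---|---|---|
| 10 | 1 | 1 | 1 |
| 15 | 1 | 2 | 1 |
| 20 | 1 | 2 | 1 |
| 30 | 1 | 3 | 1 |
| 60 | 1 | 6 | 1 |

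**Step 2: a worked night.** Take 60 minutes of REM with 24 events, one of them major. The total rate is 24/60 × 10 = 4.0 per 10 minutes, which meets the second limb. The simple/major or complex rate is 1/60 × 10 = 0.17 per 10 minutes. The night passes Section 6.2.3, fails Section 8.2 on the rate reading and passes it on the ordinary reading. So the whole question is which reading the text supports.

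**Step 3: which reading the text supports.**

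- Grammar. Remove the parenthesis and the sentence requires four episodes per 10 minutes of REM, which is the second limb of Section 6.2.3. The parenthesis then says what some of those episodes must include. The rate reading has to carry the denominator into the parenthesis. That is possible, but it is not the only literal reading.
- The rest of the sentence. It applies the test to qualifying nights. Sections 6.2.3 and 5.1 and the synopsis define that term by all three limbs, including one event per night.
- Purpose. The opening words of Section 8.2 speak of continuing to meet eligibility criteria, so they present a restatement and not a new threshold.
- Cross-references. Section 6.1 cites 6.2.3, and Section 8.1 cites 6.2 twice, once for confirming eligibility before Visit 4 and once for the central review. No section cites 8.2 as the source of the rule.

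**Step 4: what depends on it.** The full analysis set in Section 10.3.1 is defined by randomisation, dosing and evaluable primary assessments, not by deviations. The per-protocol set is defined there, but Section 10.4 assigns no efficacy analysis to it. The stated power of 0.62 rests on 34 subjects, f = 0.4 and alpha 0.05: the noncentrality is 34 × 0.4² = 5.44, and with 1 and 30 degrees of freedom the power is 0.617, which reproduces the plan's figure. The event criterion is not an input.

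**The case for a change.** The strongest reply is that the wordings do differ. Section 8.2 is headed as critical and phrased as an obligation, and the Visit 4 text does not say which section governs. Section 8.1 also defines a qualifying night of REM sleep by duration alone, so the term in Section 8.2 might not bring in the per-night limb. If the rate reading were applied, its effect would not be small. Assume Poisson counts, 60 minutes of REM and a true rate of 0.5 simple/major or complex events per 10 minutes (mean 3 for the night). About 95% of nights would then have at least 1 event, and about 8% would have at least 6. At a rate of 1.0 the figures are 99.8% and 55%; at 2.0, about 100% and 98%.

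Part of this stands: the sentence in Section 8.2 is loosely drafted. The rest carries less weight. The duration-only definition in Section 8.1 serves the decision whether to repeat the sleep study, and the same part of Section 8.1 then refers randomisation to Section 6.2. The Visit 4 wording contradicts nothing, because eligibility under Section 6.2 must already have been confirmed. The Poisson figures use assumed rates and durations and show what a disfavoured reading would do if adopted; they do not show that anyone would adopt it. For harm to follow, someone would have to apply the rate reading against the cross-references. For the per-protocol route, the result would also have to be classed as a major deviation, and the per-protocol set used for a conclusion. Section 10.4 leaves further detail to the SAP, so such a use is not excluded, but none is specified.

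**Conclusion.** The concern does not call for a change. The difference in wording is real but clerical. Section 8.2 is best read as a compressed restatement of Section 6.2.3, and on that reading the requirement is 1 event at every REM duration. On the alternative reading the gap would grow from none at 10 minutes of REM to 1 against 6 at 60 minutes, but the definition of a qualifying night and the references in Sections 6.1 and 8.1 weigh against it. This judgement is about which text the documents treat as the rule, not about which threshold is clinically preferable. It assumes that central reviewers follow the section to which they are sent.

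No effect on power, bias, the full analysis set or the primary analysis is shown. With Section 6.2.3 in use, rewording Section 8.2 would alter neither who is randomised nor how anything is scored or analysed. Tidying the sentence at a future amendment would be harmless, but nothing in the plan depends on it.
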